## Study Hypothesis

An intervention designed within the Corbin and Strauss framework can improve adherence and health outcomes compared to usual care.

**Aim 1:** Collaborative intervention development.

**Aim 2:** Cluster RCT with 500 individuals with type 2 diabetes and medication nonadherence, test the hypothesis.

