## Study Design

We will compare usual care to viewing an educational DVD including peer storytelling and a 6-month telephone-delivered peer coaching intervention. We propose to use an RCT design because we aim to test the effectiveness of the intervention on medication adherence and A1c, blood pressure and cholesterol.

The trial will be cluster-randomized to reflect the clustering of patients within tightly knit small rural communities. People talk frequently within these communities, and if two participants from the same town are in different trial arms and compare notes, this could change their behavior and threaten the validity of the study. Each of the anticipated 80-100 towns will therefore be group-randomized in blocks to avoid contamination across trial arms. We considered using physician practices as clusters, but we have learned that it is common for different family members to attend different practices many miles from home.

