## Program Descriptions

### Control Participants: General Health Videos

Participants in the control arm will receive a general health education DVD and handout. The DVD contains videos on the following topics: Dementia and Alzheimer's, Breast Cancer, Colorectal Cancer, Osteoporosis and Fall Prevention, Eye Health, Oral Health, Foot Care, and Driving Safety. A copy of the handout is included as Appendix A.

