3. During this visit, we will also make a list of all medications the participant is currently taking.
4. Provide participant with health report card

After the completion of the in-person data collection, the participant will be given the materials for the program. If the participant is in the control condition, they will be given a general health education DVD. Participants in the intervention condition will be matched with their peer advisor and given an activity book that they will use during their sessions with their peer advisors. All participants will receive their portable DVD player at the end of the data collection visit. Participants will receive a Health Report Card that provides their a1c, LDL-cholesterol, blood pressure, and weight data. If needed, participant in the intervention arm will receive a study phone.

Participants will be asked by the research staff at the in person data collection visit if they would like to use a study phone. Study phones will be taken back at the 2nd in-person study visit. Copies of the consent, in-person data collection form, and Health report card are included in Appendix F.

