### Power Calculations and Sample Size

This study is powered to detect clinically meaningful differences in changes in medication adherence, A1c, blood pressure and LDL-cholesterol between either of the intervention arms compared with the usual care arm. The secondary outcomes are based on surveys (disease acceptance, quality of life). To consider the clustering of patients within town, we used a variance inflation factor  $D = [1 + \rho(m - 1)]$ , where  $m$  is the number of participants per community and  $\rho$  is the intra-class correlation (ICC). We conservatively estimate that we will have at least 80 clusters, corresponding to an average of 6-8 participants per cluster, with ICC=0.01 and 0.05 yielding  $D=1.084$  and  $1.419$ , respectively. Dividing the sample size per group  $N$  by  $D$  gives  $N_{\text{EFF}}$ , the effective sample size. In the Encourage study, those reporting nonadherence at baseline demonstrated ICCs in the range of 0.001-0.015 for most measures. To be conservative because we include new communities, we present power calculations for ICC=0.01-0.05. We observed 20% attrition over one year in the Encourage study and although attrition is likely to be lower over 6 months, we assume 20% attrition here, leaving 200 participants per group. Table 7 displays the detectable differences in adherence proportions and the difference in mean changes between groups detectable with 80% power using 2-sided  $X^2$  and t-tests with  $\alpha=0.05$ . We used variances based on the Encourage sample reporting nonadherence at baseline. We hypothesize that the intervention will result in improved medication adherence. Because eligibility requires low adherence at baseline, we expect low acceptance at baseline. Starting with low baseline values by design eliminates ceiling effects and allows us to reasonably anticipate large changes in the intervention groups and only modest changes in the control arm, as was seen in a storytelling intervention directed at blood pressure. For  $N=200$  per group, the difference in rates of medication adherence treated as a binary outcome detectable with 80% power depends on the proportion observed in the intervention group. If adherence is only 20% in the intervention group, then we can detect as different rates among the control group of 8.8-10.1%, depending on ICC. These rates are both lower than we anticipate for the intervention group and considerably higher than we expect in the control group. Assuming 200 participants per group we will have 80% power using 2-sided t-tests to detect differences of 0.28-0.32 standard deviations for continuous outcomes. Using variance estimates from Encourage data for change in the Diabetes Distress Score, another validated psychometric instrument, this translates into detecting differences as small as 3.7-4.4% of the range. Similarly, detectable differences for change in A1c are in a clinically meaningful range from 0.41-0.48%. We anticipate detectable differences for systolic blood pressure of 3-4 mmHg, and for LDL-cholesterol of 6.7-8.1 mg/dL.

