
Project investigators will be primarily responsible for protecting the safety of the study participants and the scientific credibility of the project, and the validity of the assessment of the efficacy of the interventions used in the projects. The project investigators will also formulate recommendations relating to the selection, recruitment and retention of participants, their management, improving adherence to protocol-specified regimens, and the procedures for data management and quality control.

The entire project team will monitor success of recruitment, assess data integrity, and most importantly monitor for adverse events. Risks to study participants relate mostly to misinterpretation of what is research and what is usual care and loss of confidentiality. Project investigators will carefully evaluate how the study is described and assure that study subjects are informed not to report urgent symptoms (chest pain) through email communications. Any hospitalizations or deaths discovered by the research team will be promptly reported to the DSMB with an assessment of whether any study procedures may have contributed to these outcomes.

The risks of the study are low, and thus the safety monitoring plan has been matched to the risk to subjects in this study. Risks to physician study participants relate mostly to misinterpretation of what is research and what is usual care and loss of confidentiality. We are encouraging physicians and their staff to increase their provision of care related to diabetes, osteoarthritis and chronic pain to be consistent with current guidelines. However, we are not asking the physicians or their staff to provide services beyond those in standard, high-quality medical practices.

For this study, we plan interim data analysis twice annually to assess probability of statistically significant group differences. We will first compare baseline data to assure adequacy of randomization. We will then conduct interim analyses that will coincide with practice data intervals, and set intervals for patient data collection for outcomes data. Prior to interim analyses, investigators will assign stopping rules. Safety data to be included in these reports include hospitalization rates as well as Emergency Room utilization.

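### The comparator is called usual care but is delivered as a general health education control, and a sentence on encouraging physicians fits no described part of the trial

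*Combined protocol and SAP*

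**What the plan says.** The comparison is framed against usual care wherever the purpose of the trial is stated. The Study Hypothesis reads "An intervention designed within the Corbin and Strauss framework can improve adherence and health outcomes compared to usual care". Study Design says "We will compare usual care to viewing an educational DVD including peer storytelling and a 6-month telephone-delivered peer coaching intervention". Power Calculations and Sample Size describes differences "compared with the usual care arm". The project overview in Background and Significance and the Study Aims, including Aim 2, use the same term.

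The operational sections describe something else. Under Control Participants: General Health Videos, "Participants in the control arm will receive a general health education DVD and handout"; the DVD covers eight topics, among them eye health and foot care. In-Person Biometric Data Collection Visit says "Participants will receive a Health Report Card that provides their a1c, LDL-cholesterol, blood pressure, and weight data", and this applies to both arms, as does the portable DVD player. Participant Retention schedules three calls and three postcards for controls, one of the postcards a prompt to watch the videos.

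Safety Assessments, in a paragraph that also discusses risks to physicians as if they were study participants, says "We are encouraging physicians and their staff to increase their provision of care related to diabetes, osteoarthritis and chronic pain". The sentence goes on to tie this to current guidelines, and the next one adds that "we are not asking the physicians or their staff to provide services beyond those in standard, high-quality medical practices".

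**The concern.** A trial supports a conclusion about the comparator that participants actually received. If the hypothesis names one comparator and the programme section delivers another, the result will be reported against the wrong reference. A positive finding would be credited as benefit over usual care, and a null finding would be read as no advantage over usual care, when neither was estimated.

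The physician sentence raises a second question. A1c, blood pressure and LDL-cholesterol are primary outcomes alongside adherence, and all three depend on what is prescribed. An activity directed at prescribers, with no arm stated, would change the background against which the programme is tested. The reader cannot tell whether it is part of the trial.

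**Working it through.** **Step 1. What each arm receives** (Program Descriptions, In-Person Biometric Data Collection Visit, Participant Retention):

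| Element | Control | Intervention |
|---|---|---|
| Own medical care | yes | yes |
| Health Report Card | yes | yes |
| Portable DVD player | yes | yes |
| Staff retention calls | 3 | 2 |
| Scheduled retention postcards | 3 | 0 |
| Videos and print | general health DVD (8 topics), handout | Living Well DVD (6 lessons), activity book |
| Peer advisor contacts | none | 13-16 |

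The items particular to controls are the general health DVD and handout, three postcards and 3 − 2 = 1 extra short call. The project overview promises controls diabetes education only after the 6 months.

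**Step 2. Which contrast this gives.** Work on an additive scale relative to usual care. Let *s* be the effect of what both arms get (report card, player, two calls), *g* the effect of what only controls get, and *p* the effect of the Living Well package.

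- Trial contrast: (*s* + *p*) − (*s* + *g*) = *p* − *g*.
- Intervention arm as delivered against usual care: *s* + *p*.
- Package alone against usual care: *p*.

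The shared items cancel, so they do not by themselves bias the comparison between arms. The trial contrast still differs from the second quantity by *s* + *g* and from the third by *g*. The documents give neither *s* nor *g*. A true contrast of zero means *p* = *g*, which is compatible with *p* above zero; that is why a null result cannot be read as no better than usual care.

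**Step 3. Whether the physician sentence belongs to this trial.** In the text available, physicians and practices otherwise appear in recruitment (Recruitment Methods), in symptom reports and referral (Safety Assessments), and when a peer advisor helps a participant contact the doctor (Peer Advisor Manual, for example Sessions 4 and 5). No section describes an intervention with physicians. Osteoarthritis and chronic pain are not targets here, and the interim-analysis paragraph mentions practice data that no section collects. Background and Significance describes the team's earlier trial in diabetes with chronic pain. Carry-over is a reasonable inference but not a documented fact.

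**Step 4. What would follow if it is live.** Randomization assigns towns by zip code. Study Design explains why practices were not used as clusters: "it is common for different family members to attend different practices many miles from home". A practice could therefore see patients from both arms. An equal, additive effect in both arms would cancel as in Step 2. Narrowing needs overlap with how the package works, and there is some. Peer advisors prompt participants to ask the doctor about uncontrolled A1c, blood pressure and LDL, and Secondary Outcomes records regimens to detect intensification due to the interventions. If physicians were already intensifying treatment in controls, less would be left for the coaching to add.

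**Step 5. Sensitivity, as an assumption.** The documents give no effect for such an activity.

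- Plan's inputs: 500 × 0.8 / 2 = 200 per group; design effects 1.084 and 1.419; detectable differences 0.28 and 0.32 SD at 80% power, two-sided 0.05.
- Reproduction: effective N = 200/1.084 = 184.5 and 200/1.419 = 140.9. Detectable difference = (1.960 + 0.842) × √(2/N) = 0.292 and 0.334 SD. These are slightly larger than stated, so power at 0.28 and 0.32 SD is 76.7% and 76.6%. That gap is a separate matter.
- If the contrast at those differences were smaller by 10%, 20% or 30%, power would be about 68%, 58% or 47% under either design effect.

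This shows sensitivity only; it is not evidence that any narrowing occurs.

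**The case against.** The strongest reply is that this is an ordinary attention control. The control videos include no listed diabetes or medication-adherence content, every participant must have a primary care doctor, and nothing withdraws that care. The contents of both arms are set out openly, Data Analysis speaks of control patients and a control arm, and Study Design already names the DVD and coaching together, so a whole-package reading is available. All of that stands. It shows that the design is legitimate and the analysis unaffected; it does not make the comparator usual care in the hypothesis, aims and power text.

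On the physician sentence, the reply is that it is limited to guideline-consistent, standard care and is probably leftover text. The limit is real and must be read with the sentence. It does not settle the matter, because the text still speaks of increasing care, and the Background describes an area short of primary care, where standard high-quality care may exceed what patients usually get.

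Three stronger readings are tempting and not supported. A reader might infer that no arm receives usual care; controls keep their own care, with attention and feedback added. A reader might infer that the physicians of all participants, in both arms, are being prompted; no arm or reach is stated, and Study Design does not say that any practice serves both arms. A reader might try to convert the control materials into a lost A1c effect; no such figure is given, and the report card, the player and most of the staff calls are common to both arms.

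**Conclusion.** The point holds as one of naming and reconciliation. The trial estimates the Living Well package against general health education with retention contact, where both arms also receive biometric feedback and a DVD player. It does not estimate benefit over usual care in either direction, and it does not separate the Corbin and Strauss framework from the rest of the package. The randomised comparison itself is not biased by this.

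The size of the gap between the stated and the delivered contrast cannot be computed, because the documents give no effect for the control materials, the contacts or the feedback. The physician sentence has a consequence only if it is live and overlaps with the coaching; the power range above is conditional on both. The statement that it matches no other component rests on the part of the document available, which does not include Appendices D to G.

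**What to change.** 1. In the project overview of Background and Significance, and in Study Aims, Study Hypothesis, Study Design and Power Calculations and Sample Size, replace usual care with the comparator as delivered: a general health education control (DVD, handout, retention calls and postcards) on top of the participant's own care, with the Health Report Card and DVD player common to both arms.
2. State the planned conclusion as the effect of the whole Living Well package (diabetes education, stories, coaching) against that comparator.
3. Reconcile Safety Assessments with the rest of the protocol. If the sentences on encouraging physicians and on physicians as participants come from another project, remove them. If they describe a real activity, state what is done, with which practices and in which arms.

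The cost is wording in the protocol and SAP. Randomisation, sample size, data collection and analysis need no change on account of the comparator. The downside is a less attractive claim than superiority to usual care.

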## Process Measures

A careful assessment of intervention implementation can provide insights into which aspects of the intervention were particularly effective. We will use cell phones provided by the study to track the frequency and amount of time spent on coaching sessions, as well as how closely they were implemented on schedule. Additional process measures will come from the peer coach Workbooks for each participant. These will include notes from each session as well as data entered for specific activities. We provide a chapter from our current trial’s Peer Coach Workbook in the Appendix to give a general idea of how these workbooks capture process data. We also monitor intervention implementation on an ongoing basis through weekly teleconferences with peer coaches, and weekly outreach to each peer coach individually throughout the intervention period. We provide updates on the progress of the study, collaboratively troubleshoot problems, and provide ongoing advice, which often stems from other peers or the community coordinators. We also address specific concerns with the help of our community coordinators (e.g., finding participants whose telephone numbers have changed).

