## **Safety Assessments**

This study does not involve any new treatments of care, but rather focuses on standard care delivered in a new way. It is possible that the interventions will result in better compliance with medication treatment, resulting in over-control of diabetes or blood pressure. This could result in low blood sugar or low blood pressure and resultant symptoms. Therefore, we will monitor potential adverse events of this nature. We will monitor symptoms of low blood sugar in both trial arms at the follow-up data collection point as well as at ongoing contacts during the 12-week intervention phase, by peer coaches. During these contacts, symptoms of low blood sugar and low blood pressure will be assessed and reported to the investigators and to the participant's physician. If symptoms are present, the peer coach will refer participants to their primary care provider for evaluation immediately, assisting with the telephone call if needed.

Data on safety endpoints will be reviewed by a board convened for this purpose. Quarterly reports will be presented to the board over the course of the trial. The board will be constituted by 3 individuals experienced in the conduct of clinical trials and the safety of human subjects. Adverse events will be reported to the UAB IRB, and the NIH Office of Biotechnology Activities (OBA) in accordance with regulations, by the PI.

[name] and project investigators, including our community team members, will have an initial organizational meeting or conference call to discuss the protocol development, review of scientific, safety and ethical issues

related to the study design and approve plans for data integrity. After the initial planning meeting project investigators will be convened monthly in a meeting or conference call throughout the project period.

[name] will be responsible for monitoring the safety and efficacy of the study, executing the data and safety monitoring plan, and complying with the reporting requirements. She will provide a summary of the DSM report to PCORI on an annual basis as part of the progress report. The report will include participant's sociodemographic characteristics, expected versus actual recruitment rates, any quality assurance or regulatory issues that occurred during the past year, summary of adverse events, and any actions or changes with respect to the protocol. The DSM report to PCORI will also include, when available, the results of any efficacy data analysis conducted.

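### Interim efficacy comparisons between arms are planned twice a year by the study team, with no stated limit on who sees them, while the same investigators advise on recruitment and retention

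*Combined protocol and SAP*

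**What the plan says.** All the relevant text is in the Safety Assessments section of the combined protocol and SAP.

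- **The analyses.** "For this study, we plan interim data analysis twice annually to assess probability of statistically significant group differences". A baseline comparison comes first. The later analyses are tied partly to "set intervals for patient data collection for outcomes data", so outcomes are meant and not only safety counts.
- **The decision rule.** "Prior to interim analyses, investigators will assign stopping rules". No rule or boundary is given.
- **Who monitors efficacy.** One named person "will be responsible for monitoring the safety and efficacy of the study, executing the data and safety monitoring plan".
- **What the funder receives.** "The DSM report to PCORI will also include, when available, the results of any efficacy data analysis conducted". That report is annual.
- **What the board receives.** "Data on safety endpoints will be reviewed by a board convened for this purpose". It has three members and quarterly reports, and is also told of hospitalizations and deaths.
- **What else the investigators do.** "The project investigators will also formulate recommendations relating to the selection, recruitment and retention of participants". The section says that the project investigators include community team members and meet monthly.

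**The concern.** The issue is who learns the emerging result and what they can still change. How much alpha each look spends is a separate matter.

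The arms are not concealed from those delivering the trial, recruitment is rolling, and the primary analysis is of self-reported adherence. The Primary Outcomes section itself says self-report is open to recall and social desirability bias. Under the Randomization section, a town's first enrollee fixes the arm for every later resident, so a recruiter can know the arm before approaching the next person in that town.

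If the team also knows which arm is ahead, it could change whom it approaches, how hard it pursues follow-up in each arm, or how it presents the programme. Later data could then move toward or away from the trend. A stopping boundary controls repeated testing but does not undo changed behaviour. A1c, blood pressure and LDL-cholesterol are measured by device, so they are less exposed to reporting bias, but selection and retention could still affect them.

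**Working it through.** The plan gives no figure for this point. The core of the check is a reading of the text, followed by a timing calculation and an illustration.

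**Step 1: duties side by side.** The interim comparison, the stopping rules and efficacy monitoring all sit with the study team or a named individual. The board's stated task is safety endpoints. Advice on selection, recruitment and retention sits with the project investigators. The sections on power, data analysis and safety name no independent analyst, closed report or restriction on results by arm. The list of appendices contains no monitoring charter. The overlap between those who can see results and those who can act on them follows from the plan as written.

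**Step 2: how much of the trial lies after the first informative look.** The project overview gives 500 participants recruited in years 2 and 3, with follow-up at 6 months. I assume even accrual over 18 to 24 months and looks every 6 months. At month 6 essentially no 6-month outcomes exist, so the first informative look is at month 12, when those enrolled by month 6 have reached follow-up.

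| | 18-month accrual | 24-month accrual |
|---|---|---|
| Outcomes in at month 12 | 500 × 6/18 = 167 | 500 × 6/24 = 125 |
| Outcomes outstanding | 500 − 167 = 333 (67%) | 500 − 125 = 375 (75%) |
| Enrolled at month 12 | 500 × 12/18 = 333 | 500 × 12/24 = 250 |
| Not yet enrolled | 500 − 333 = 167 (33%) | 500 − 250 = 250 (50%) |

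These counts are before attrition. Even attrition would leave the percentages unchanged.

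**Step 3: illustration of what a shift would do.** Suppose there is no true effect and changed behaviour adds an average difference s in adherence between arms. With 200 per arm after attrition (500 × 0.8 / 2):

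- SE = √{[p(1−p) + (p+s)(1−p−s)] / (200/D)}
- False-positive rate = P(|Z| > 1.96), where Z has mean s/SE

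The inputs are p = 0.10 to 0.30 (assumed) and D = 1.05 and 1.26. The D values come from 500/80 = 6.25 people per town at ICC 0.01 and 0.05: 1 + 0.01 × 5.25 and 1 + 0.05 × 5.25. The larger factors printed in the sample-size section would lower the rates slightly.

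- s = 0.02, p = 0.10, D = 1.05: SE = √(0.1956/190.5) = 0.0320, mean 0.62, rate 9.6%.
- s = 0.02, p = 0.30, D = 1.26: SE = √(0.4276/158.7) = 0.0519, mean 0.39, rate 6.7%.
- s = 0.03, same two settings: 15.1% and 8.9%.

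The shift s is an average over all outcomes, but only 67-75% of them follow the look. Two points overall therefore needs 2/0.75 to 2/0.667 = 2.7 to 3.0 points among those, and three points needs 4.0 to 4.5. If recruitment were the only route, two points overall would need 2/0.50 to 2/0.333 = 4 to 6 points among people not yet enrolled. No document supports any particular value of s.

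**The case against.** Several objections have force.

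**The trial is open anyway.** Selective recruitment and enthusiastic coaching are possible with no interim look, and routine retention contacts are scheduled in advance for each arm. This stands in part. Only the additional risk from knowing the trend can be put down to the interim plan, and it cannot be separated from the rest. Knowing a participant's arm is still different from knowing which arm is ahead.

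**The text may be carried over from another study.** The section refers to physician participants, osteoarthritis and chronic pain, and practice data, none of which fits this trial. The practice-data phrase is in the interim paragraph itself. The section also mentions a data and safety monitoring plan, which may be a separate document containing access rules. Both possibilities are real, but the interim plan is stated as current and needs correction or clarification in either case.

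**The board may see efficacy.** A reader might infer that the board is independent and barred from efficacy data. The text says neither. It calls the members experienced, gives them safety endpoints, and leaves unclear who receives the reports that carry interim safety data. The supportable statement is narrower: no text gives the board the efficacy comparison or confines that comparison to it.

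**The funder and the coaches.** A reader might infer that the funder gets results by arm twice a year. The report is annual, includes efficacy when available, and does not say by arm. A reader might also infer that coaches hear results, because the Process Measures section says: "We provide updates on the progress of the study, collaboratively troubleshoot problems, and provide ongoing advice". That paragraph concerns implementation of the intervention, and nothing in it shows outcome results reaching coaches. I do not rely on it.

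**Conclusion.** The concern holds in a limited form. As written, the plan lets people who advise on recruitment and retention learn the between-arm trend while 67-75% of outcomes are outstanding at month 12, assuming even accrual over 18 to 24 months. It states no restriction that would prevent this. That the team itself runs the analyses is read from the first-person wording, the stopping-rule sentence and the efficacy-monitoring duty; no analyst is named.

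The size of any resulting bias cannot be derived from the documents. A reader might take 6.7-9.6% or 8.9-15.1% as the trial's false-positive rate, but those figures only show what assumed shifts of 2 or 3 points would do. The change is worth making because it is cheap. Nothing here shows that bias would occur.

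**What to change.** In the Safety Assessments section, drop the interim efficacy comparison by arm. Keep the safety reports, including hospitalization and emergency room use, and state that they go to the board. Withhold efficacy results by arm from the annual funder report until follow-up is complete.

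If efficacy looks are kept, send them as a closed report to the existing three-person board only, under a stopping rule fixed before the first look. The report should be prepared by someone with no role in recruitment, coaching or data collection, and everyone else should see pooled data. The section would also need to say that the board's remit covers efficacy and that its members are outside the project team, since it says neither now.

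The first option costs only wording and a change to the report template. The second also needs an analyst outside the investigator team, whom the documents do not provide. Under both, the team and the funder wait until the end for comparative results.
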